8.3.3 Pediatric Quality of Life Inventory (PedsQL)

The PedsQL is a validated instrument that consists of generic core scales suitable for use with pediatric populations, including those with acute or chronic health conditions. The PedsQL will be administered only in countries where a translated version is available and will be completed at Visit 3, Visit 6, and at ETV in case of early termination. The version of the PedsQL used at Visit 3 should be consistent with the subject's age at Visit 3, and should be maintained for each subject for the duration of the study. Section 3.2.16 details how the scores for the core domains are calculated.

The PedsQL completed at Visit 3 will be considered Baseline as it is expected that this will be completed prior to the first dose of study medication.

8.3.3.1 Pediatric Quality of Life Inventory (PedsQL) Ages 1-12 Months

The multidimensional PedsQL 1-12 months generic core scales encompass the following core domains for pediatric HRQoL measurement: Physical Functioning, Physical Symptoms, Emotional Functioning, Social Functioning, and Cognitive Functioning.

Calculated values and changes from Baseline for the total scale score (all scales), the psychosocial health summary score, the physical health summary score and each of the 5 scale scores will be summarized for each visit, as appropriate, by treatment group. A change from Baseline will only be calculated if the same version of the PedsQL was completed at Baseline and at the corresponding post-Baseline visit.

All PedsQL 1-12 months data will be listed.

8.3.3.2 Pediatric Quality of Life Inventory (PedsQL) Ages 13-24 Months

The multidimensional PedsQL 13-24 months generic core scales encompass the following core domains for pediatric HRQoL measurement: Physical Functioning, Physical Symptoms, Emotional Functioning, Social Functioning, and Cognitive Functioning.

Calculated values and changes from Baseline for the total scale score (all scales), the psychosocial health summary score, the physical health summary score and each of the 5 scale scores will be summarized for each visit, as appropriate, by treatment group. A change from Baseline will only be calculated if the same version of the PedsQL was completed at Baseline and at the corresponding post-Baseline visit.

All PedsQL 13-24 months data will be listed.

8.3.3.3 Pediatric Quality of Life Inventory (PedsQL) Ages 2-4 years

The multidimensional PedsQL 2-4 years generic core scales encompass the following core domains for pediatric HRQoL measurement: Physical Functioning, Emotional Functioning, Social Functioning, and School Functioning.

Calculated values and changes from Baseline for the total scale score (all scales), the psychosocial health summary score, the physical health summary score and each of the 4 scale scores will be summarized for each visit, as appropriate, by treatment group. A change from Baseline will only be calculated if the same version of the PedsQL was completed at Baseline and at the corresponding post-Baseline visit.

All PedsQL 2-4 years data will be listed.

8.3.4 Concomitant medical procedures

Subjects who had any concomitant medical procedures during the course of the study based on the Concomitant Medical Procedures eCRF will be listed. These will be attributed to the Baseline Period and Treatment Period based on the date of the procedure. Any partial dates reported for dates of the procedures will be imputed as described in Section 4.2.5.

Additionally, subjects who had any procedures or surgeries prior to study entry based on the Procedure History eCRF will also be listed.

The number of concomitant medical procedures per subject will be summarized by treatment group for the Baseline Period and the Treatment Period, separately. The number of concomitant medical procedures per subject will also be summarized using the categories 0, 1, 2, and 3 or

Healthcare provider consultations not foreseen by the protocol will be attributed to the Baseline. Period and Treatment Period based on the date of the consultation. Any partial dates reported for dates of the consultations will be imputed as described in Section 1.2.

The number of healthcare provider consultations per subject during the Baseline Period and during the Treatment Period will be summarized, separately, by treatment group. The number of healthcare provider consultations will also be summarized using the categories 0, 1, 2, and 3 or

The number of healthcare provider consultations during the Baseline Period and during the Treatment Period will be summarized, separately, by type of provider (General Practitioner, Specialist Physician, Nurse, or Other) and treatment group. Percentages will be relative to the number of healthcare provider consultations during the Baseline Period and during the Treatment Period, respectively.

All healthcare provider consultations data will be listed.

Hospital stays and ER visits

Hospital stays and ER visits will be attributed to the Baseline Period and Treatment Period based on admission date. Any partial dates reported for admission dates will be imputed as described in Section 4.2.5.

The number of hospital stays per subject during the Baseline Period and during the Treatment Period will be summarized, separately, by treatment group. The number of hospital stays will also be summarized using the categories 0, 1, 2, and 3 or more. The number and percentage of subjects with specific reasons for hospital stays will be summarized for the duration of the Baseline Period and for the duration of the Treatment Period, separately, by treatment group.

Duration of hospital stays (as defined in Section 3.2.17) during the Baseline Period and during the Treatment Period will be summarized, separately, by treatment group. Duration of hospital stays will also be categorized as 0 days, 1-5 days, 6-10 days, 11-15 days, and >15 days, and summarized for the duration of the Baseline Period and the duration of the Treatment Period, separately, by treatment group.

An event logged on the Hospitalization/ER Visit eCRF module where ER is marked as initial entry point will be defined as an ER visit. An ER visit with a subject transfer to an inpatient general ward will also be counted as a hospitalization. However, all other instances of ER visits (where subject transfer is not to an inpatient general ward) will not be counted as hospitalizations. Descriptive statistics for the number of ER stays for the duration of the Baseline Period and for the duration of the Treatment Period will be presented, separately, by treatment group. The number of ER visits will be tabulated using the categories 0, 1, 2, and 3 or more, and summarized by treatment group for the duration of the Baseline Period and for the duration of the Treatment Period. The number and percentage of subjects with specific reasons for ER visits

Lacosamide

will be summarized for the duration of the Baseline Period and for the duration of the Treatment Period, separately, by treatment group.

Descriptive statistics of LCM plasma concentrations

CM plasma concentrations will be summarized

o the same number of places as the clude number of entired. Hospitalizations with either a partial admission or discharge date are ignored for the calculation of duration of hospital stay. However, such hospitalizations are counted for the number of hospital stays. Subjects with no hospital stays within a study period will have a duration of 0 days for that period. Should distinct records for hospital stays overlap, then the days during the overlap will only be counted once. Similarly, this also applies for ER visits.

All hospitalization and ER data will be listed.

9

9.1

The results of LCM plasma concentrations will be summarized using all reported decimal places and displayed to the same number of places as they are recorded in the database. Descriptive statistics will include number of subjects (n), number of subjects with plasma levels above lower limit of quantification (LOQ), arithmetic mean, SD, coefficient of variation (CV[%]), geometric mean, geometric CV(%), median, minimum, and maximum. The maximum number will be reported to 4 decimal places for any summary statistics. The CV(%) and geometric CV(%) will be presented with 1 decimal place.

Summary statistics will only be calculated if at least 2/3 of data are above the lower LOQ. Values which are less than the lower LOQ will be set to LOQ/2 for the determination of all summary statistics.

Summary tables of LCM plasma concentrations will be presented by treatment group, visit including the Last Visit, and time point for the PK-PPS. Summaries will also be performed by LCM maintenance dose level and repeated by LCM maintenance dose level and age group.

A listing of LCM plasma concentrations by age group will be presented. In addition, and as appropriate, listings of concomitant AED plasma concentrations and last intake of concomitant AEDs prior to blood sampling by age group will be presented.

Population pharmacokinetics 9.2

A population PK analysis will be performed in NONMEM. The data will be added to data from other studies; methods will be described in a DAP (Data Analysis Plan) and the results will be reported separately from SP0967.

SAFETY ANALYSES 10

All safety variables will be analyzed using descriptive methods on the SS.

10.1[©] **Extent of exposure**

The overall duration of study medication exposure (defined in Section 3.2.6) during each of the Titration Period, Maintenance Period, and Treatment Periods will be calculated, as follows:

Titration Period: date of last dose of study medication during the Titration Period minus the date of first dose of study medication plus 1.

Statistical Analysis Plan

Maintenance Period: date of last dose of study medication during the Maintenance Period minus the date of first dose of study medication during the Maintenance Period plus 1.

Treatment Period: date of last dose of study medication during the entire Treatment Period minus

The median total daily dose (mg/kg/dav) during the Treatment Particle of the study during the Treatment Particle of the study during the levels defined above by treatment group, and repeated by treatment group and age group, using the levels defined in Section 3.2.7.

Treatment Period will be summarized by treatment group, and repeated by treatment group and age group, using the levels defined in Section 3.2.7.

In addition, for the Titration Period, the number of back titration steps for each subject (categorized as: 0, 1, 2, and 3 or more), and the number of subjects with a dose change together with the number of dose changes during the interval by dose back titration occurred (categorized as: $\frac{4mg}{kg} \frac{day}{day} \ge 4 - \frac{6mg}{kg} \frac{day}{day} \ge 6 - \frac{8mg}{kg} \frac{day}{day} \ge 10 - \frac{12mg}{kg} \frac{day}{day}$ and >12mg/kg/day) will be summarized by treatment group, and repeated by treatment group and age group using the levels defined in Section 3.2.7.

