5 STUDY DESIGN

5.1 Study description

SP0967 is a Phase 3, multicenter, double-blind, randomized, PBO-controlled, parallel-group study to evaluate the efficacy and safety of LCM 8mg/kg/day to LCM 12mg/kg/day as adjunctive therapy in subjects ≥ 1 month to < 4 years of age with epilepsy with partial-onset seizures.

Primary and secondary efficacy variables will be based on video-EEGs (up to 72 hours of continuous recording with every attempt to obtain at least 48 hours of interpretable recording). The video-EEGs will be conducted in an inpatient setting. Assessment of video-EEG seizure count will be performed locally by the investigator, subinvestigator, or qualified designated reader for the purpose of both assessment of eligibility and study analyses.

Baseline Period

At Visit 1 (Day -7), subjects who meet the selection criteria will begin a 7-day Baseline Period (Day -7 to Day -1). In the event that additional time is needed to access inpatient facilities to perform the video-EEG, a maximum of 7 days may be added to the period between Visit 1 and 2. From Visit 2 (Day -3 to Day -1) to Visit 3 (Day 1), an End-of-Baseline Period video-EEG will be performed.

After completion of the End-of-Baseline video-EEG at Visit 3, subjects who meet the selection criteria will be randomized in a double-blind manner to 1 of 2 parallel treatment arms: LCM or PBO in a 1:1 ratio.

Titration Period

Subjects will begin a 20-day blinded Titration Period (Day 1 to Day 20) to attain the target dose for the Maintenance Period (LCM 8mg/kg/day to LCM 12mg/kg/day, or matching PBO).

Subjects will be dispensed study medication and will begin treatment with LCM oral solution 4mg/kg/day or matching PBO for 4 days. Subjects will then be titrated at 4-day intervals as recommended in Table 7-1. The current 4-day titration step approach has been selected as it is generally accepted that frequent seizures require a rapid titration of AEDs.

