5.1.1 Study duration per subject

For each subject, the maximum total study duration can be up to 93 days (not withstanding visit windows), including the 30-day Safety Follow-Up Period. Each subject's participation in the study begins with a 7-day Baseline Period (no administration of study medication). Each subject's maximum total duration of study medication administration in SP0967 can be up to 55 days. This includes a 20-day Titration Period, a 7-day Maintenance Period, a 12-day Transition Period (for subjects who plan to enter the open-label extension study [EP0034]) and/or up to a 16-day Taper Period (for subjects who will not be entering EP0034).

The end of the study is defined as the date of the last visit of the last subject in the study.

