3.2.2 Study periods

This study consists of the following six periods: Baseline Period, Titration Period, Maintenance Period, Transition Period, Taper Period, and Safety Follow-Up Period. Additionally, for analysis purposes, the Treatment Period includes Titration and Maintenance Periods. Each period is defined in turn as follows for the classification by study period:

Baseline Period

This is defined as the period from the date of Visit 1 (entry to study) to 1 day prior to the date of first dose of study medication. In addition, pre-dose scheduled assessments which are performed on the date of first dose of study medication will be assigned to the Baseline Period. Any unscheduled assessments which are performed prior to the date of first dose of study medication will also be assigned to the Baseline Period.

Titration Period

This is defined as the period of time from the date of first dose of study medication to the last Titration Period visit date (Telephone Contact 3 [T3]) for subjects who complete the Titration Period, or from the date of first dose of study medication to the date of the Early Termination Visit (ETV) for subjects who prematurely discontinue prior to the last Titration Period visit date (T3). If a subject does not have a T3/ETV, then either the date of the last scheduled or unscheduled visit during the Titration Period or the date of last known dose of study medication, if this is after the last scheduled or unscheduled visit date during the Titration Period, will define the end date of the Titration Period.

Maintenance Period

This is defined as the period of time from the day after the end date of the Titration Period (T3) to the last Maintenance Period visit date (Visit 6 [Day 27]) for subjects who complete the Maintenance Period, or from the day after the end of the Titration Period (T3) to the date of the ETV for subjects who prematurely discontinue prior to the last Maintenance Period visit date last scheduled or unscheduled visit during the Maintenance Period or the date of last known dose of study medication, if this is after the last scheduled or unscheduled or Maintenance Period, will define the end date of the Maintenance Period.

Treatment Period

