This is defined as the period of time from the date of first dose of study medication to the last Treatment Period visit date (Visit 6 [Day 27]) for subjects who complete the Treatment Period, or from the date of first dose of study medication to the date of the ETV for subjects who prematurely discontinue prior to the last Treatment Period visit date (Visit 6 [Day 27]). If a subject does not have a Visit 6 (Day 27)/ETV, then either the date of the last scheduled or unscheduled visit during the Treatment Period or the date of last known dose of study medication, if this is after the last scheduled or unscheduled visit date during the Treatment Period, will define the end date of the Treatment Period.

Transition Period

For those subjects who complete the Maintenance Period and plan to participate in the open-label extension study (EP0034), the Transition Period is defined as the date after the end of the Maintenance Period (Visit 6 [Day 27]) to the date of Transition Visit 2.

Taper Period

For those subjects who discontinue study medication or for those subjects who complete the Maintenance Period but choose not to enter EP0034, the Taper Period is defined as the date after the end of the Titration, Maintenance or Transition Period, whichever is later, to the date of the Taper Visit.

Safety Follow-Up Period

There will be a 30-day Safety Follow-Up Period for subjects not entering EP0034. The start of the Safety Follow-Up Period is defined as the day after the last dose of study medication in SP0967 and continues until the date of last telephone contact and/or 30 days after the last dose of study medication, whichever is later.

Mapping of assessments performed at Early Termination Visit

Efficacy and safety assessments at an ETV that correspond to a scheduled visit will be summarized at the scheduled visit corresponding to the ETV if the assessment was scheduled to Occur at that visit. Such assessments will also be considered for Last Visit.

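### Healthcare resource counts in SAP 8.3.4 to 8.3.6 take no account of days observed, although the Baseline Period is 7 to 14 days and the Treatment Period is 27 days or less

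*SAP*

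**What the plan says.** Healthcare resource use is the last of the other efficacy variables in Protocol 4.1.3, and Protocol 13.1.3 promises descriptive statistics by treatment group. The SAP supplies the detail.

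- **Procedures (SAP 8.3.4):** "The number of concomitant medical procedures per subject will be summarized by treatment" group, for the Baseline and Treatment Periods separately, and again in categories of 0, 1, 2, and 3 or more.
- **Consultations (SAP 8.3.5):** the same layout.
- **Hospital stays and emergency visits (SAP 8.3.6):** "The number of hospital stays per subject during the Baseline Period and during the Treatment" Period, with the same categories. Days in hospital are also banded (0, 1-5, 6-10, 11-15, more than 15), with identical bands for both periods. A child with no stay in a period is given 0 days for it, however long the child was observed.

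The periods differ in length.

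- **Baseline:** Protocol 5.1 says "subjects who meet the selection criteria will begin a 7-day Baseline Period (Day -7 to Day -1"), but "a maximum of 7 days may be added to the period between Visit 1 and 2". SAP 3.2.2 includes any such extension: "This is defined as the period from the date of Visit 1 (entry to study) to 1 day prior to the date of" first dose.
- **Treatment:** by SAP 3.2.2, "the Treatment Period includes Titration and Maintenance Periods". Protocol 5.1.1 gives the lengths: "This includes a 20-day Titration Period, a 7-day Maintenance Period, a 12-day Transition Period", and so on. For early leavers SAP 3.2.2 closes the period sooner: "or from the date of first dose of study medication to the date of the ETV for subjects who" discontinue prematurely.

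For these variables neither document has a rate, a person-time denominator or a restriction to completers.

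**The concern.** A count per child measures how often care was used multiplied by how long the child was watched. Here the second factor differs between the two periods for every child. It differs between children in Baseline because of the permitted extension, and between children in the Treatment Period because of early termination. A child who leaves on Day 9 without an event is tabulated exactly like one who is event-free for 27 days.

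Two readings of the tables are therefore exposed. A reader who sets the Baseline table beside the Treatment table will see a rise even if nothing has changed. A reader who compares arms within the Treatment Period is comparing unequal observation time if the arms lose children at different rates. What is at stake is the interpretation of a listed descriptive variable, not any tested endpoint.

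**Working it through.** **Period length.** Titration 20 days + Maintenance 7 days = 27 days, which reproduces the Treatment Period length in the heading of Protocol Table 5-1. Baseline is 7 days, or 7 + 7 = 14 with the full extension. Visit windows are ignored.

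**Between periods.** At a constant daily rate the expected count is proportional to days observed, so the apparent fold change is Treatment days divided by Baseline days.

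- Completer, 7-day Baseline: 27/7 = 3.86.
- Completer, 14-day Baseline: 27/14 = 1.93.
- All children, with 14% leaving early (the overall dropout in Protocol 13.6) at a mean day of 5 to 20 (assumed): mean Treatment time is 0.86 × 27 + 0.14 × 5 = 23.92 days to 0.86 × 27 + 0.14 × 20 = 26.02 days. The ratio is 3.42 to 3.72 for a 7-day Baseline and 1.71 to 1.86 for a 14-day Baseline.

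The category tables are affected in the same way. With an assumed rate of 0.02 events per day and Poisson counts, the chance of at least one event is 1 − exp(−0.02 × days): 13.1% over 7 days, 24.4% over 14 and 41.7% over 27.

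**Between arms, Treatment Period.** Mean days observed = (1 − d) × 27 + d × L, where d is the share leaving early and L is their mean leaving day. The documents give about 14% overall dropout (Protocol 13.6) and a 24% ceiling at re-estimation (Protocol 13.5), with no split by arm. The splits below are assumptions that average 14%; the wider one puts one arm at 24%. L is ranged from 5 to 20. Example: (1 − 0.18) × 27 + 0.18 × 5 = 23.04.

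| Early leavers, arm A v arm B | L | Mean days A | Mean days B | B/A at equal daily rates |
|---|---|---|---|---|
| 14% v 14% | 5 to 20 | 23.92 to 26.02 | same | 1.000 |
| 10% v 18% | 5 | 24.80 | 23.04 | 0.929 |
| 10% v 18% | 20 | 26.30 | 25.74 | 0.979 |
| 4% v 24% | 5 | 26.12 | 21.72 | 0.832 |
| 4% v 24% | 20 | 26.72 | 25.32 | 0.948 |

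Counts in the arm with more leavers are thus 2% to 7% lower in the first unequal split and 5% to 17% lower in the second.

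**When the direction reverses.** If leavers use care at k times the daily rate of the others, a leaver's expected count equals a completer's when k × L = 27, that is k = 27/L: 5.4 at L = 5, 2.7 at L = 10, 1.93 at L = 14 and 1.35 at L = 20. Above that value the arm with more leavers shows higher counts.

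**With a rate.** At 0.02 events per day, 0.14 events over 7 days, 0.28 over 14 and 0.54 over 27 all become 0.56 per 28 subject-days. At a constant rate the period ratio and the arm ratio are both 1.0, whatever the Baseline length or the early leaving.

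**The case against.** The strongest reply is that the troublesome comparison is never planned. The SAP summarises the two periods separately by treatment group and specifies no change, ratio or test for these variables; where it wants change from Baseline, as for the PedsQL, it says so. Randomised arms compared within one period are untouched by the difference between the periods. This stands: the apparent rise is a misreading that the layout invites, not an analysis the sponsor has promised.

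Some context is already available. Exposure during the Treatment Period is summarised by arm (SAP 10.1), disposition is shown by study period and arm (SAP 5.1), and the individual events are listed. A careful reader could detect unequal follow-up between arms. Baseline length, however, is not summarised, and none of this is brought together with the counts. The split of consultations by provider type uses consultations as its denominator, so period length does not drive it. If inpatient stays for the protocol video-EEG were logged in both periods, the fold for hospital stays would shrink; the variable is defined as unrelated to the study, but SAP 8.3.6 states no exclusion.

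Three stronger readings are tempting and are not supported.

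- A reader might infer that lacosamide will look favourable because tolerability withdrawals will fall in that arm. The documents give no arm-specific dropout, and Protocol 6.3 also requires withdrawal for generalized convulsive status epilepticus, which could remove children on placebo.
- A reader might infer that one arm will look cheaper. No costs are analysed.
- A reader might infer that the band above 15 days is impossible in Baseline. Stays are attributed by admission date (SAP 8.3.6) and run to discharge (SAP 3.2.17) with no cut at the period end, so a long stay that starts in Baseline can be tabulated there.

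**Conclusion.** The point holds as a minor one. The counts in SAP 8.3.4 to 8.3.6 do not allow for time observed. At a constant daily rate, period length alone makes a completer's Treatment count 1.9 to 3.9 times the Baseline count, so the two sets of tables cannot be read against each other. Within the Treatment Period, a difference between arms arises only if early leaving differs. Under the assumed splits it is about 2% to 17% at equal daily rates; it is 0 with equal dropout and can reverse if leavers use more care per day. The period ratio rests on lengths stated in the documents and the constant-rate assumption. The arm figures also rest on dropout splits and leaving days that the documents do not give. The variable is descriptive, and no primary or secondary result depends on it.

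**What to change.** In SAP 8.3.4 to 8.3.6, add two rows for each period and arm: total days observed, and the event rate per 28 subject-days (total events divided by total days observed, times 28). Use the period start and end dates already defined in SAP 3.2.2. State that any between-period or between-arm remark will rest on the rate, and keep the counts and categories as supporting rows.

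If days in hospital are also given as a rate, count only the days that fall inside the period. Otherwise a stay that runs past the period end would put days in the numerator that the denominator does not contain.

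The cost is SAP wording and one or two extra rows per table. No data collection, study procedure or primary analysis changes. The rate removes the effect of unequal observation time. It does not remove any real difference in care use between children who leave and children who stay, so days observed should be shown beside it.
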